11.6. Planned Sample Size

9 to 24 subjects

Rationale:

In this study, DLT evaluation will be conducted in at least 3 subjects per cohort in principle, and the safety of DS-3032b at doses up to 160 mg will be confirmed in Subtrial A unless the completion criteria provided in “Section 5.3.2 Definition of Maximum Tolerated Dose” are met. If no DLT occurs in any of the cohorts before the 160 mg cohort, the total number of subjects in this study will be the minimum. In this case, a total number of 9 subjects, consisting of 3 subjects each in the 90 mg, 120 mg, and 160 mg cohorts, will participate in the study. For instance, if 6 subjects participate in each of the 90 mg, 120 mg, and 160 mg cohorts, the total number of subjects participating in the study will be 18. Also, if two or more dosing schedules are assessed, the total number of subjects may be further increased.

11.7. Details of Modified Continual Reassessment Method

The details of mCRM used for explorative dose finding in Subtrial A will be provided in this section, unless otherwise noted.

11.7.1. Bayesian Logistic Regression Model

The following BLRM will apply to the dose-response relationship for DLTs:

$$\text{logit}(\pi(d)) = \log(\alpha) + \beta \log(d/d^*), \alpha > 0, \beta > 0,$$

where $\text{logit}(\pi(d)) = \ln(\pi(d) / (1 - \pi(d)))$, $\pi(d)$ is the DLT rate at a dose of d , and d^* is 160 mg. As a consequence, $\log(\alpha)$ is equal to $\text{logit}(\pi(d^*))$ at the dose of d^* . Note that if the dose is zero, the DLT rate is also zero. If other dosing schedules are assessed, d^* will be set separately based on the information obtained up to that time.

11.7.2. Prior Distribution of Bayesian Logistic Regression Model

Assuming that BLRM model parameters $\log(\alpha)$ and $\log(\beta)$ follow bivariate normal distribution, a minimally informative prior distribution is set as follows. If other dosing schedules are assessed, each parameter will be set separately based on the information obtained up to that time.

Parameter	Mean	Standard Deviation	Correlation Coefficient
$\log(\alpha), \log(\beta)$	(-1.8999, 1.3484)	(2.2792, 1.3727)	-0.3157

The above parameters for a prior distribution will be calculated as shown below.

- Based on the overseas Phase 1 study (U102), the median probability of the DLT rate was estimated to be 5% and 20% for the 120 mg qd 21/28 day schedule and the 160 mg qd 21/28 day schedule, respectively.
- From the ratio (0.67) of the dosing days in this study to U102, the median probability of the DLT rate is assumed to be 3% and 13% at doses of 120 mg and 160 mg, respectively, in this study.
- Based on the median probability of the DLT rate at the above doses, parameters of the bivariate normal distribution will be calculated to generate vague prior Bayesian intervals (to minimize prior information) using minimal information beta distribution.

11.7.3. Recommended Dose for the Next Cohort by Bayesian Logistic Regression Model Incorporating the Escalation with Overdose Control Principle

The recommended dose in the next cohort is decided based on posterior distribution of the DLT rate at planned doses (90 mg, 120 mg, and 160 mg). After completing DLT evaluation in 3 subjects per cohort in principle, posterior distribution of the DLT rate at each planned dose will be estimated using BLRM based on the results of DLT evaluation and prior distribution set in “[Section 11.7.2 Prior Distribution of Bayesian Logistic Regression Model](#),” and posterior probability of the DLT rate falling under the following four intervals will then be calculated for each planned dose. The following posterior probabilities can also be calculated for other doses than the planned, as long as the dose is more than 1.3 times but not more than 2 times of the dose in the concerned cohort.

- [0, 16%]: DLT rate interval for under-dosing
- (16, 33%]: target DLT rate interval
- (33, 60%]: DLT rate interval for excessive toxicity
- (60, 100%]: DLT rate interval for unacceptable toxicity

Among the planned doses and additional candidate doses, the dose with posterior probability of 25% for the DLT rate exceeding 33% (probability for excessive and unacceptable toxicity) (according to the EWOC principle) and with the highest posterior probability for the DLT rate being more than 16% and 33% or less (probability for target DLT rate interval) will be chosen as the recommended dose for the next cohort. The EWOC principle will apply from the third cohort. Dose increments for the next cohort should be within the 1.3-fold and 2-fold range.

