3.1. Starting Dose in Each Subtrial

The dose of DS-3032b for Cohort 1 in Subtrial A will be 90 mg (see “[Section 5.2.3 Rationale for the Dose and Regimen](#)”).

The starting dose in the subtrial that has a smaller number of dosing days than the subtrial in which the MTD has been determined will be equal to or lower than the MTD in the subtrial in which the MTD has been determined. For instance, when the MTD in Subtrial A is determined to be 120 mg, the starting dose in Subtrial B will be 120 mg or 90 mg.

The starting dose in the subtrial that has a greater number of dosing days than the subtrial in which the MTD has been determined will be lower than the MTD in the subtrial in which the MTD has been determined. For instance, when the MTD in Subtrial A is determined to be 160 mg, the starting dose in Subtrial D will be 120 mg or 90 mg. When the MTD has not been reached in Subtrial A, the starting dose in Subtrial D will be equal to or lower than the maximum dose used in Subtrial A.

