3.2. Explorative Dose Finding in Each Subtrial

After confirming the DLT rate in Cycle 1 in each cohort in accordance with “Section 5.3.1 Definition of Dose-limiting Toxicities,” the dose for the next and subsequent cohorts will be determined, in consideration of the following i) and ii). As a rule, each cohort consists of 3 to 6 subjects, and if “Section 5.4 Enrollment of Additional Subjects” is applicable, enrollment of additional subjects will be considered.

- i) Recommended dose, guided by mCRM using a Bayesian logistic regression model (BLRM) incorporating the EWOC principle
- ii) Clinical evaluation of the toxicological profile and information on pharmacokinetics/pharmacodynamics (PK/PDy)

Rationale:

The study design was selected in reference to the “Guidelines for Clinical Evaluation of Anticancer Drugs.¹⁷” The Bayesian statistical analysis methods are specified in “Section 11.7 Details of Modified Continual Reassessment Method.”

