5.2. Method of Study Treatment

5.2.1. Dose

The starting dose of DS-3032b in Subtrial A will be 90 mg. The subsequent doses will be determined, taking the following into consideration.

- i) Recommended dose, guided by mCRM using a BLRM incorporating the EWOC principle
- ii) Clinical evaluation of the toxicological profile and information on PK/PD_y

Dose increments should be at least 1.3-fold in order to make a distinction among the dose cohorts, considering inter-subject variability in exposure. Even if the recommended dose for the next cohort calculated by the model is more than 2-fold, the dose should be no more than 2-fold.

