5.3.2. Definition of Maximum Tolerated Dose

If any of the following completion criteria are met, the MTD will be determined based on comprehensive evaluation of the recommended dose guided by mCRM incorporating the EWOC principle, and safety and PK/PDy information of DS-3032b.

Completion criteria:

- DLT evaluation is completed in at least 15 subjects in the entire study and in at least 6 subjects in the cohort of the dose selected to be the dose for the next cohort by mCRM.
- DLT evaluation is completed in at least 6 subjects in the cohort of the dose selected to be the dose for the next cohort by mCRM, with at least 50% posterior probability for the DLT rate ranging between 16% and 33%.
- DLT evaluation is completed in at least 3 subjects in the cohort of each dose, with no DLTs reported.
- The posterior probability for the DLT rate of 33% or higher in the 90 mg cohort is at least 60%.

5.3.3. Study Treatment to Subjects in Each Cohort and Procedure for Proceeding to the Next Cohort

In the cohort of the first dose, study treatment for the second subject must be started after an at least 1-week interval from the first dose of treatment in the first subject. In the subsequent cohorts, study treatment for the next subject may be started on the following day of the start day of study treatment in the first subject.

If proceeding to the next cohort involves an increase in the dose, study treatment for the first subject in the new cohort will be started after the end of the DLT evaluation period in at least 3 subjects in the ongoing cohort. If a DLT occurs in 2 subjects before registration of the third subject, the dose for the third subject will be reviewed by using the mCRM incorporating the EWOC principle.

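### In Subtrial A the dose rule in 11.7.3 recommends 160 mg after 0/3 DLTs at 90 mg, so the 90-120-160 mg path and minimum of 9 in 11.6 depend on overriding the model

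*Combined protocol and SAP*

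**What the plan says.** All references are to the combined protocol and SAP.

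- **Dose rule (11.7.3).** Among the planned doses (90, 120, 160 mg) and any additional candidates, the recommended dose is the one "with the highest posterior probability for the DLT rate being more than 16% and 33% or less", subject to a 25% limit on the probability that the DLT rate exceeds 33%. That limit starts late: "The EWOC principle will apply from the third cohort".
- **Step size (5.2.1, 11.7.3).** Increments must be at least 1.3-fold, and "the dose should be no more than 2-fold". No sentence forbids passing over a planned dose. Section 5.2.3 gives 160 mg/day as the planned maximum.
- **Role of the model (3.2, 5.2.1).** "the dose for the next and subsequent cohorts will be determined, in consideration of the following i) and ii"): the model recommendation is input i), and clinical toxicity with PK/PDy information is input ii).
- **Sample size (11.6).** If no DLT occurs before the 160 mg cohort, the total is the minimum: "a total number of 9 subjects, consisting of 3 subjects each in the 90 mg, 120 mg, and 160 mg cohorts".
- **Third completion criterion (5.3.2).** "DLT evaluation is completed in at least 3 subjects in the cohort of each dose, with no DLTs reported".
- **Scope (11.7).** "The details of mCRM used for explorative dose finding in Subtrial A will be provided in this section".

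**The concern.** Section 11.6 describes a step-by-step climb through three levels and takes the minimum sample size from it. A reader would expect the rule in 11.7.3 to produce that climb when no toxicity is seen. If it does not, two things follow. A team that follows the recommendation gives the second cohort the planned maximum dose, with no data at 120 mg and before the overdose limit applies. And the stated minimum of 9 is not what the rule gives.

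The clinical background does not settle whether skipping is acceptable. The Japanese study in solid tumors and lymphomas (1.3.2) had DLTs at 120 mg and an MTD of 90 mg on the 21/28 schedule. The overseas study in hematological malignancies (1.3.1), which is the source of the prior, had an MTD of 160 mg on 21/28. That is 160 × 21 = 3,360 mg per cycle, against 160 × 14 = 2,240 mg for 160 mg on the 14/28 schedule of Subtrial A.

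**Working it through.** **Inputs.** Model (11.7.1): logit π(d) = log α + β log(d/160). Prior (11.7.2): (log α, log β) bivariate normal, means −1.8999 and 1.3484, SDs 2.2792 and 1.3727, correlation −0.3157. Target interval (16%, 33%]; overdose means above 33%. The posterior was computed on a numerical grid and checked by simulation; independent runs agreed to about 0.003.

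**Reproducing the plan's own figures.** The prior medians come out at 3.1% (120 mg) and 13.0% (160 mg), against the stated 3% and 13%; at 90 mg the median is 1.0%. The minimum of 3 + 3 + 3 = 9 reproduces only if the 90-120-160 mg path is taken as given.

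**Choosing the second cohort's dose, after 0/3 at 90 mg.**

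| Dose | P(target) | P(rate > 33%) |
|---|---|---|
| 90 mg | 0.044 | 0.016 |
| 120 mg | 0.082 | 0.043 |
| 130 mg | 0.097 | 0.060 |
| 150 mg | 0.136 | 0.117 |
| 160 mg | 0.164 | 0.173 |

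The rule takes the largest P(target), which is at 160 mg. The step is 160/90 = 1.78, inside the cap. Had the 25% limit applied already, 0.173 would pass it. With 0/6 at 90 mg the choice is the same (about 0.15 against 0.06 at 120 mg).

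**Continuing with no DLTs.** After 0/3 at 160 mg, P(target) is 0.030 at 120 mg and 0.111 at 160 mg, so the rule stays at 160 mg. The total then depends on how the third completion criterion is read:

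- All three planned doses must have been evaluated (the reading 11.6 supports): the criterion is never met, and the first criterion (at least 15 subjects, at least 6 at the selected dose) ends the subtrial at 3 + 12 = 15. By then P(target) at 160 mg is 0.020, so the second criterion (at least 50%) cannot end it sooner.
- Only opened doses count, once 160 mg is reached: 3 + 3 = 6.

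Neither is 9.

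**Operating figures.** Exact binomial enumeration with the model followed at every step, cohorts of 3, planned doses only, the limit read as not more than 25% from the third cohort, and at most 24 subjects. If no dose passes the limit, 90 mg is assumed.

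At the prior-median rates (1/3/13%):

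- The second cohort is at 160 mg in 0.99³ = 97.0% of trials.
- Mean sample size is 15.1 (all-doses reading) or 9.3 (opened-doses reading), against 11.7 with a one-level step limit.
- The chance of at least 2 DLTs in a cohort of 3 at 160 mg is 3 × 0.13² × 0.87 + 0.13³ = 4.6%. Multiplied by the chance of reaching 160 mg, it is 4.6% as written and 4.5% with the limit.

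At higher rates, which are assumptions and not in the documents:

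| Rates at 90/120/160 mg | Reach 160 mg: as written / limited | ≥2 DLTs in first 160 mg cohort: as written / limited |
|---|---|---|
| 5/12/25% | 91.8% / 75.5% | 14.3% / 11.8% |
| 8/18/35% | 83.4% / 57.1% | 23.5% / 16.1% |
| 10/25/45% | 76.6% / 39.9% | 32.6% / 17.0% |

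The last column is the reach column times a constant for each row (for example 0.766 × 0.425 = 0.326), so it is not separate evidence. Averaged over the vague prior in 11.7.2, the chance of at least 2 DLTs in the first 160 mg cohort is 10.3% as written and 6.9% with the limit.

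**The case against.** A reader might infer that 11.6 and 11.7.3 contradict each other. The documents do not support that. Sections 3.2 and 5.2.1 make the recommendation one of two inputs, 11.6 never says that its path is model output, and the DLTs at 120 mg in the Japanese study give input ii) a reason to stop at 120 mg. The 9-subject path can therefore be reached within the written procedure. This part of the objection stands. What remains is that the no-DLT scenario on which the minimum is built needs the model to be set aside at the first decision.

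Further points that stand in part:

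- The 15-subject path needs a sponsor who follows the model mechanically and never opens 120 mg, although 3 DLT-free subjects there would end the subtrial. The fall in mean sample size from 15.1 to 11.7 should not be claimed as a saving.
- The 160 mg ceiling comes from 5.2.3, not 11.7.3. Without it, 170 or 180 mg would score slightly higher in the second cohort (0.179 and 0.175). No reading brings back 120 mg.
- The larger safety contrasts rest on assumed rates, the effect on correct MTD selection was not computed, and Cycle 1 is inpatient.
- Section 11 defers detail to a separately prepared analysis plan. A step limit could stand there; the text reviewed has none.

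**Conclusion.** The point holds as a mismatch in Subtrial A between the prespecified rule and the sample-size rationale. With the stated prior and 0/3 at 90 mg, the rule recommends 160 mg by about 0.16 to 0.08, and with no DLTs it never recommends 120 mg. This rests on the planned doses, a 160 mg maximum, no overdose limit at the second cohort and the 2-fold cap. It does not depend on the true DLT rates or on the exact wording of the 25% limit.

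A reader might also infer that the plan is unsafe or that its sample-size range is wrong. Neither follows. At the prior medians the safety difference is 4.6% against 4.5%; it grows only if true rates are higher than the sponsor expects. Mean sample sizes at all the fixed rates examined lie inside the planned 9 to 24. The matter is worth fixing because it arises after the likeliest first result and the repair is short.

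**What to change.** Add to 11.7.3: *In Subtrial A, escalation may not skip a planned dose (90, 120, 160 mg) that has not been evaluated, and no step may exceed the next higher planned dose.* In the third completion criterion of 5.3.2, write *each planned dose (Subtrial A: 90, 120 and 160 mg)*.

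With no DLTs the rule then gives 120 mg (0.082 against 0.044 at 90 mg), next 160 mg (about 0.15 against 0.04 at 120 mg, overdose probability 0.11), and stops at 9, as 11.6 states.

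Leave the other subtrials to be set when they open. Section 3.1 lets a later subtrial start above 90 mg (for example, "the starting dose in Subtrial B will be 120 mg or 90 mg" if the Subtrial A MTD is 120 mg), and a blanket criterion could send it back to a dose it did not need.

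**Cost.** Up to one extra cohort of 3 before 160 mg. At the prior medians, mean sample size rises from 9.3 to 11.7 if the third criterion would otherwise count only opened doses. The sponsor also loses first-step candidates between 120 and 160 mg, such as 130 and 150 mg, which 11.7.3 now allows. A protocol amendment is needed. This version is dated 07 Oct 2019 and the study period ends on 31 Dec 2019, so the second-cohort decision may already have been taken; that is an inference.

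If skipping 120 mg is intended, leave 11.7.3 as it is and correct the path and the minimum in 11.6. In either case, state the overdose condition as *not more than 25%*.

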DS3032-A-U102 was a Phase 1, multicenter, open-label study of DS-3032b. This study, consisting of Part 1 (dose escalation) and Part 2 (dose expansion), was conducted in subjects with advanced hematological malignant tumors (AML, acute lymphocytic leukemia [ALL], chronic myelogenous leukemia [CML], and high-risk myelodysplastic syndrome [MDS]) to evaluate the safety and tolerability of DS-3032b, to assess the MTD or RP2D of DS-3032b, and to evaluate the pharmacokinetics/pharmacodynamics of DS-3032b. As of 17 Oct 2016, 37 subjects with AML or high-risk MDS have been enrolled and treated with DS-3032b in the dose escalation part (Part 1), and the study is currently underway. In Part 1, DS-3032b was administered once daily on Days 1 to 21, followed by a 7-day rest, in a 28-day cycle (qd 21/28 day schedule), starting from 60 mg and escalating through 90, 120, 160 and 210 mg, guided by mCRM with EWOC. DLTs were reported as Grade 3 hypokalemia in 1 subject and Grade 3 diarrhea in 1 subject at 160 mg. At 210 mg, DLTs were reported as Grade 2 acute renal failure (less than 75% of the specified number of dosing days in Cycle 1), Grade 3 nausea and vomiting, and Grade 3 fatigue and anorexia in 1 subject each.¹³ Based on these results, MTD for the qd 21/28 day schedule was determined to be 160 mg. In the efficacy assessment, a decrease in bone marrow blasts ($\geq 50\%$ decrease from baseline in 10 of 15 subjects) was observed in 15 of 26 subjects who underwent bone marrow assessment 28 days after the first dose of DS-3032b (after the end of the first cycle). CR was achieved in 2 subjects with relapsed or refractory AML who were treated with DS-3032b at 120 mg qd for 4 months or 160 mg qd for 13 months, and CR as determined by bone marrow assessment was achieved in 1 subject with high-risk MDS who was treated with DS-3032b at 120 mg qd for 4 months.¹³

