1.3.2. Japanese Phase 1 Study (Study DS3032-A-J103)

DS3032-A-J103 is a Phase 1 dose-ascending study of DS-3032b in Japanese subjects with advanced solid tumors or lymphomas. The objectives of the study were to evaluate the safety and tolerability of DS-3032b, assess the MTD or RP2D of DS-3032b, and evaluate the pharmacokinetics and pharmacodynamics of DS-3032b.

In this study, DS-3032b was administered once daily on Days 1 to 21, followed by a 7-day rest, in a 28-day cycle (qd 21/28 day schedule), starting from 60 mg and escalating through 90 mg and 120 mg, guided by mCRM with EWOC. As of 31 Oct 2016, a total of 18 subjects have been enrolled and treated in the study, and the study is currently underway. DLTs were reported in subjects treated at 120 mg, and the MTD for the qd 21/28 day schedule was determined to be 90 mg.

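### The cohort 2 waiver of the 25% overdose limit also covers escalation: harmless at 3 or 6 evaluable subjects, but after exactly 1 DLT in 4 or 5 at 90 mg the model recommends 120 mg above the limit

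*Combined protocol and SAP*

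**What the plan says.** Section 11.7.3 runs the model "After completing DLT evaluation in 3 subjects per cohort in principle". Among the candidate doses it takes "the dose with posterior probability of 25% for the DLT rate exceeding 33" percent and, of those, the one most likely to lie in the target interval. The next statement is "The EWOC principle will apply from the third cohort". Steps must be between 1.3-fold and 2-fold, and section 5.2.3 sets a planned maximum of 160 mg.

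On cohort size, section 3.2 says "As a rule, each cohort consists of 3 to 6 subjects", and section 5.3.3 asks for at least 3 subjects through the DLT period before an escalation. Section 5.3.2 ends dose finding if "The posterior probability for the DLT rate of 33% or higher in the 90 mg cohort is at least 60" percent. Section 5.3.3 adds an early check: "If a DLT occurs in 2 subjects before registration of the third subject, the dose for the third subject will be reviewed" with the model and EWOC.

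The synopsis and sections 3.2 and 5.2.1 describe the guidance as incorporating EWOC and mention no exception. They also make the model one of two inputs, beside clinical and PK/PDy evaluation.

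**The concern.** A waiver in the second cohort has one clear use. After a DLT among few subjects, the vague prior can push even the current dose past 25%, and without relief the trial could not repeat it. That reason does not extend to a higher dose. As written, the waiver lets the model recommend an escalation that its own overdose rule would bar, even when the current dose passes that rule. A colleague who has read only the synopsis or section 5.2.1 would assume that a recommended 120 mg had met the limit. The next subjects' DLT risk is at stake, so the question is whether any permitted cohort 1 outcome triggers this, and by how much.

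**Working it through.** **Inputs.** Model (11.7.1): logit π(d) = log α + β·log(d/160). Prior (11.7.2): (log α, log β) bivariate normal, means (−1.8999, 1.3484), SDs (2.2792, 1.3727), correlation −0.3157. Planned doses 90, 120 and 160 mg. The 25% is read as a maximum.

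**Reproducing the plan's figure.** This prior gives median DLT rates of 3.1% at 120 mg and 13.0% at 160 mg, against the 3% and 13% stated in 11.7.2.

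**Formulas.** After y DLTs in n subjects at 90 mg, the posterior is proportional to prior × π(90)^y × (1 − π(90))^(n−y). For each dose, target = P(0.16 < π(d) ≤ 0.33) and over = P(π(d) > 0.33). Both come from grid integration; weighted draws from the prior agree to about 0.1 percentage point.

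**Results (%).**

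| DLTs/n at 90 mg | Target at 90 / 120 / 160 | Over at 90 | Over at 120 | Cohort 2 pick as written | Pick with the limit on |
|---|---|---|---|---|---|
| 0/3 | 4.4 / 8.2 / 16 | 1.6 | 4.3 | 160 mg (over 17.3) | 160 mg |
| 1/3 | 29.1 / 27.8 / 22 | 31.2 | 47.5 | 90 mg | none admissible |
| **1/4** | 29.8 / 31.1 / 25 | 20.9 | **37.4** | **120 mg** | 90 mg |
| **1/5** | 28.7 / 32.8 / 28 | 13.9 | **29.8** | **120 mg** | 90 mg |
| 2/5 | 34.2 / 24.7 / 16 | 47.6 | 67.0 | 90 mg | none admissible |
| 1/6 | 26.5 / 33.3 / 29 | 9.3 | 24.0 | 120 mg | 120 mg |
| 2/6 | 39.0 / 30.4 / 20 | 36.3 | 58.1 | 90 mg | none admissible |

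With 0/4, 0/5 and 0/6 the pick is 160 mg at 16.0, 15.0 and 14.3%, within the limit. With 2/3, 2/4 and 3/6 the value at 90 mg is 76.2, 61 and 69.7%, so the 60% completion criterion is met.

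Only 1/4 and 1/5 escalate past the limit. The trade is 31.1 − 29.8 = 1.3 points of target probability for 37.4 − 20.9 = 16.5 points of overdose probability after 1/4, and 32.8 − 28.7 = 4.1 points for 29.8 − 13.9 = 15.9 after 1/5.

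**Unplanned doses.** Between 1.3 × 90 = 117 mg and 160 mg, the 30 and 100 mg capsules (5.2.2) make 120, 130, 150 and 160 mg. Target probability at 130 mg is 29.9% after 1/4 and 32.0% after 1/5, below that at 120 mg, and it falls further above that. The pick stands.

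**Next 3 subjects, posterior predictive, 120 v 90 mg.**
- After 1/4: expected DLTs 0.87 v 0.61; chance of 2 or more, 24% v 15%.
- After 1/5: expected DLTs 0.76 v 0.51; chance of 2 or more, 20% v 11%.

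**Frequency.** Under the protocol's prior each outcome has about 11% probability, given that cohort size. If cohort 1 is read at 4 or 5 in 10 to 50% of cases (an assumption; the documents give nothing), the overall chance is 0.10 × 11% to 0.50 × 11%, about 1 to 5%. The prior expects few DLTs at 90 mg. For an assumed true rate there of 10 to 33%, 1/4 has probability 29 to 42% and 1/5 has 33 to 41%, again given that size.

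**The case against.** The strongest reply is that the case is rare and buffered. Three subjects is the default, section 11.6 illustrates cohorts of 3 or 6, and neither size triggers the problem. Apart from replacing non-evaluable subjects, section 5.4 sends extra enrolment to discussion between investigator and sponsor, so an unusual cohort size would probably be seen. The model only advises, and subjects are in hospital in Cycle 1. On the 1 to 5% range and about 0.25 extra expected DLTs, the average cost is roughly 0.003 to 0.013 DLTs per trial. This stands, and it sets the priority. The early check in 5.3.3 is no help here: it needs 2 DLTs, and these outcomes have 1.

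The second reply is that 120 mg is defensible. The posterior median DLT rate there is 25% after 1/4 and 22% after 1/5, inside the target interval. In the overseas AML/MDS study behind the prior, "MTD for the qd 21/28 day schedule was determined to be 160 mg", with no DLTs reported at 120 mg on that longer schedule. Against that, in the Japanese solid tumor and lymphoma study "DLTs were reported in subjects treated at 120 mg" and the MTD was 90 mg, also on 21/28. The evidence is mixed. It does not make 120 mg unsafe, but it gives no reason to suspend the plan's own limit when 90 mg satisfies it.

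The third reply is that a bare restriction can backfire. If 1/4 is followed by a new cohort of 3 at 90 mg, there is a 41% chance (29.0 + 11.7) of 1 or 2 further DLTs. No planned dose is then within 25% (90 mg is at 27.3% for 2/7 and 58.6% for 3/7) and the 60% criterion is not met. If 120 mg is given instead, the chance of that impasse is 18%. After 1/5 the figures are 9% and 20%. This stands, and it is why the filling step below has to be mandatory.

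**Conclusion.** The gap is real, narrow and of low priority. In Subtrial A, exactly two permitted cohort 1 outcomes, 1/4 and 1/5 at 90 mg, lead the model to recommend 120 mg at 37.4% or 29.8% overdose probability while 90 mg meets the limit. This rests on the stated prior, the 25% read as a maximum, and doses capped at 160 mg. How often cohort 1 would be read at 4 or 5 is unknown.

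A reader might infer more, and the documents do not support it:
- That cohort 2 generally escalates without overdose control. At 3 or 6 subjects every escalation the model recommends is within 25%.
- That the waiver should be deleted. After 1/3 or 2/6 no planned dose passes, and the waiver is what lets 90 mg be repeated.
- That over-limit dosing would follow. Clinical and PK/PDy review can hold 90 mg.
- That the 25% printed without an inequality sign is a defect. The sign may have been lost when the PDF was read, and the meaning is clear.

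**What to change.** Replace the waiver sentence in 11.7.3 with:

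> The 25% limit applies in every cohort to any dose higher than the current dose; for the second cohort only, the current dose may be repeated when it does not meet the limit, provided the 60% completion criterion in 5.3.2 is not met. If the limit bars escalation after exactly 1 DLT in 4 or 5 evaluable subjects in cohort 1, the cohort will be filled to 6 and the model rerun before the cohort 2 dose is chosen.

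Among the planned doses, only the 1/4 and 1/5 decisions change. Filling resolves each of them at the cohort 2 decision:
- After 1/4, 2 more subjects give 0 DLTs in 66% (1/6: 120 mg opens at 24.0%), 1 in 27% (2/6: 90 mg at 36.3%, repeat allowed) and 2 in 7% (3/6: 69.7%, criterion met).
- After 1/5, 1 more subject gives 0 DLTs in 83% (1/6) and 1 in 17% (2/6).

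The cost is 2 or 1 more subjects at 90 mg, within the 3 to 6 of section 3.2, and a delay of one 28-day DLT period plus recruitment time in these two outcomes. In most of them escalation to 120 mg still follows, later and within the limit.

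The change does not remove every impasse. As under the current text, 1/3 followed by 1/3 at 90 mg (30% chance after 1/3) leaves 90 mg at 36.3% at the cohort 3 decision, with no planned dose admissible and the 60% criterion unmet.
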